8.8 Impact of COVID-19 Pandemic

Summaries and analyses to describe and/or assess the impact of the COVID-19 pandemic will be included in a future amendment to this plan and/or provided in the study report. These may include tabulations of COVID-19 related protocol deviations and patterns of missing data, summaries of COVID-19 AEs, the addition of a per-protocol population, and comparative analyses of selected endpoint before, during and after the pandemic.

9 IDENTIFICATION AND SUMMARY OF PROTOCOL DEVIATIONS

Important protocol deviations as pre-specified in the study Protocol Deviation Management Plan. In accordance with ICH E3, Important eligibility deviations (as documented on study CRFs and Important post-randomization protocol deviations tracked in the study clinical trial management system (CTMS) will be identified and listed separately by study center and subject. Important deviations will be summarized for the PITT and ITT populations by deviation code (a standardized description e.g. “did not satisfy eligibility criteria” or “received prohibited medication”)

10 DATA QUALITY ASSURANCE

The Clinical, Data Management, Biostatistics, and Medical Writing departments at Exelixis and designees will work diligently and collaboratively to ensure that the data collected and analyzed for this study are of the highest quality. Controls including Case Report Form (CRF) design, CRF annotation, database design, data-entry processes, data validation programs, discrepancy management, consistent use of medical coding, data extraction processes, and database locking processes ensure the quality of the data. These controls are assessed at regular intervals during a trial.

Appendix A: Date Imputation Rules

Incomplete Cancer Diagnosis Date

If *year* is missing (or completely missing): do not impute

If only *day* is missing: set to 15th of the month.

If *day* and *month* are missing: set to July 1st.

If either imputation rule above results in a diagnosis date > informed consent:

set diagnosis date to the date of informed consent - 1.

Incomplete Adverse Event Onset Date

Assumption: For on-study Adverse Events.

If *year* is missing (or completely missing): set to the date of first dose.

If (*year* is present and *month* and *day* are missing) or (*year* and *day* are present and *month* is missing):

If *year* = year of first dose: set the date to the first dose date.

If *year* < year of first dose: set *month* and *day* to December 31st.

If *year* > year of first dose: set *month* and *day* to January 1st.

If *month* and *year* are present and *day* is missing:

If *year* = year of first dose, and:

If *month* = month of first dose: set *day* to day of first dose.

If *month* < month of first dose: set *day* to last day of *month*.

If *month* > month of first dose: set *day* to 1st day of *month*.

If *year* < year of first dose: set *day* to last day of month.

If *year* > year of first dose: set *day* to 1st day of month.

For all other cases: set to date of first dose.

Incomplete Concomitant Medication Start Date

If *year* is missing (or completely missing): do not impute.

If (*year* is present and *month* and *day* are missing) or (*year* and *day* are present and *month* is missing):

Set *month* and *day* to January 1st.

If *year* and *month* are present and *day* is missing:

Set *day* to 1st day of month.

Incomplete Concomitant Medication End Date

If *year* is missing (or completely missing): do not impute.

If (*year* is present and *month* and *day* are missing) or (*year* and *day* are present and *month* is missing):

Set *month* and *day* to December 31st.

If *year* and *month* are present and *day* is missing:

Set *day* to last day of the month.

Incomplete Subsequent Anticancer Therapy Start Date

Assumption: Anticancer therapies reported on the Subsequent Anticancer Therapy CRF.

If *year* is missing (or completely missing): set to date decision to discontinue study treatment + 1

If (*year* is present and *month* and *day* are missing) or (*year* and *day* are present and *month* is missing):

If *year* > year of date of decision to discontinue study treatment: Set *month* and *day* to January 1st.

If *year* = year of date of decision to discontinue study treatment: Set *month* and *day* to date of decision to discontinue study treatment + 1

If *year* and *month* are present and *day* is missing:

Set *day* to 1st day of month if the resulting imputed date is greater than date of decision to discontinue study treatment or if the month is before the month of date of decision to discontinue study treatment and year is same or before the year of the date of decision to discontinue study treatment. Otherwise set the imputed date to date of decision to discontinue study treatment + 1

Incomplete Death Date

Identify date of last known alive (LA) prior to death from the following:

1. Date of decision to discontinue study treatment from End of Treatment CRF
2. Date of last radiographic assessment from End of Radiographic Follow Up CRF
3. Date last known alive from Survival Follow Up CRF
4. Date of last lab assessment from the Labs dataset

If *year* is missing (or completely missing): set to date of LA + 1

If only *day* is missing: set to the maximum of the first of month or LA + 1

If *month* and *day* are missing:

If *year* of LA = *year* of death

Set death date to date of LA + 1

If *year* of most-recent contact < *year* of death

Set *month* and *day* to Jan 1st.

Incomplete Study Treatment Start Date

Define previous sequential dosing “milestone” as the latest of previous dose stop date, previous dose hold stop date, date of first dose or randomization date.

If *year* is missing (or completely missing): set to date of previous sequential dosing “milestone” + 1

If (*year* is present and *month* and *day* are missing) or (*year* and *day* are present and *month* is missing): set to January 1st

If *year* and *month* are present and *day* is missing: set to the first day of the month

If the imputed date is before the previous sequential dosing “milestone”: set to the date of previous sequential dosing “milestone” + 1

Incomplete Study Treatment Stop Date

Define next sequential dosing “milestone” as the earliest of next dose start date, next dose hold start date, date of last dose from EOT CRF or the cutoff date.

If *year* is missing (or completely missing): set to date of next sequential dosing “milestone” - 1

If (*year* is present and *month* and *day* are missing) or (*year* and *day* are present and *month* is missing): set to December 31st

If *year* and *month* are present and *day* is missing: set to the last day of the month

If the imputed date is after the next sequential dosing “milestone”: set to the date of next sequential dosing “milestone” - 1

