5.8.6.2. Routine Tumor Assessment

Radiographic response and disease progression will be determined using RECIST version 1.1 ([Appendix E](#)). For the purpose of determination of the radiographic study endpoints, central review of radiographic images will be conducted by a BIRC. All radiographic tumor assessments will be promptly sent to the BIRC, which also will review prior radiation history data for the purpose of selection of target lesions. Sites will be provided with instructions for how images should be collected and submitted to the BIRC. Study staff shall ensure that no images contain personal data as defined by applicable local, regional, and international laws and regulations.

Radiographic tumor assessments will include the following:

1. **Chest / Abdomen / Pelvis (CAP):** CT of CAP or CT chest and MRI abdomen/pelvis will be performed in all subjects at screening (prior to randomization). Tumor assessments after randomization should be performed every 6 weeks (\pm 7 days) through Week 49. After Week 49, these assessments will be performed every 12 weeks (\pm 7 days). CT/MRI of the CAP should include a noncontrast study of at least the liver followed by contrast with triphasic CT imaging of the liver or liver MRI with gadolinium enhanced imaging including triphasic liver.
2. **Other sites:** All other known or suspected sites of disease, including in the brain or bone, are to be imaged by CT/MRI at screening (prior to randomization). Any lesions identified, including bone lesions with a soft tissue component, are to be followed at subsequent tumor assessments as described for CAP above using the same modality as at screening. New suspected lesion sites identified after randomization, including suspected sites of bone or brain lesions, should be assessed by CT/MRI. MRI is the preferred method for brain lesion assessment. If CT of the brain is performed instead of MRI, ambiguous results must be confirmed by MRI. (Note: in order to meet the eligibility requirements of the study, brain metastasis must have been treated and stable for at least 8 weeks before randomization. Subjects without documented brain metastasis during the screening assessment are not required to undergo post-randomization brain imaging unless clinically indicated.)

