7.1.1.4 Primary Definition

For the primary analysis directed toward the primary estimand, duration of PFS is defined as the time from randomization to the earlier of either the date of radiographic progression per BIRC or the date of death due to any cause.

PFS (months) = (earliest date of progression, death, censoring – date of randomization + 1)/30.4375

General censoring rules for the primary analysis of PFS are described below, with details provided in Table 7Table 8 (analysis ID PFS-EP-1):

- Subjects who receive systemic or local NPACT or non-protocol radiation therapy (other than to bone) or surgery to resect target lesions before experiencing an event will be right censored at the date of the last tumor assessment prior to the date of initiation of subsequent therapy/surgery. If there is no such tumor assessment post randomization, the subject will be right censored on the date of randomization.
- Subjects who have not experienced an event (and are not otherwise censored) at the time of data cutoff will be right censored on the date of their last tumor assessment post randomization that is on or prior to the data cutoff date. If there is no such tumor assessment post randomization, the subject will be right censored on the date of randomization.
- Subjects who miss 2 or more scheduled tumor assessments followed by an event will be right censored on the date of their most-recent tumor assessment prior to the missing assessments. If there is no such tumor assessment post randomization, the subject will be right censored on the date of randomization.

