All sensitivity and supplemental analyses will include all subjects in the PITT population. Tabulated summaries of survival times, hazard ratios, and log rank test statistics as well as graphs of survival functions will be presented.

Table 8: Event and Censoring Rules for Primary and Sensitivity Analyses of Primary PFS Estimand

Estimand	Primary		Primary		Primary		Primary	
Analysis type	Primary		Sensitivity		Sensitivity		Sensitivity	
Analysis purpose	Primary		Evaluate assessment time bias		Evaluate assessor bias		Evaluate potentially informative censoring	
Analysis ID	PFS-EP-1		PFS-EP-2		PFS-EP-3		PFS-EP-4	
Analysis name	rPFS per BIRC		Uniform dates		rPFS per Investigator		rPFS per BIRC despite missing ATA	
Estimand endpoint	Radiographic PD		Radiographic PD		Radiographic PD		Radiographic PD	
Population	PITT		PITT		PITT		PITT	
Situation	Outcome	Date of Outcome	Outcome	Date of Outcome	Outcome	Date of Outcome	Outcome	Date of Outcome
Radiographic PD per RECIST 1.1 per BIRC	event	date of recorded PD	event	date of scheduled visit (or next scheduled visit if between visits)	NA	NA	event	date of recorded PD
Radiographic PD per RECIST 1.1 per Investigator	NA	NA	NA	NA	event	date of recorded PD	NA	NA
Death	event	date of death	event	date of death	event	date of death	event	date of death
Intercurrent events (excluding those with Treatment Policy strategy for all estimands)								
Clinical deterioration	NA	NA	NA	NA	NA	NA	NA	NA
Systemic NPACT (medications)	censored	date of last ATA* before first initiation of therapy	censored	date of last ATA* before first initiation of therapy	censored	date of last ATA* before first initiation of therapy	censored	date of last ATA* before first initiation of therapy
Local NPACT (medications)	censored	date of last ATA* before first initiation of therapy	censored	date of last ATA* before first initiation of therapy	censored	date of last ATA* before first initiation of therapy	censored	date of last ATA* before first initiation of therapy
Surgical resection of target tumor lesion(s)	censored	date of last ATA* before target lesion resection	censored	date of last ATA* before target lesion resection	censored	date of last ATA* before target lesion resection	censored	date of last ATA* before target lesion resection

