7.1.2.6 Supportive Analyses

A supportive analysis (OS-EA1-1) directed at the alternative estimand will be conducted in the experimental and control arms in the ITT population. In this analysis a subject receiving non-protocol systemic or local-liver directed anticancer therapy (medications) will be right censored at the first start date of such subsequent anticancer therapy. Summaries will be provided as for

the primary analysis of OS.

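### SAP Appendix A tests month and year separately for day-missing anticancer therapy start dates, so some starts in an earlier calendar year are imputed to the day after the discontinuation decision

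*SAP*

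**What the plan says.** The rule is in SAP Appendix A, under the heading for incomplete subsequent anticancer therapy start dates. Its scope is "Assumption: Anticancer therapies reported on the Subsequent Anticancer Therapy CRF". When year and month are known and the day is missing, there are three branches:

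- A: keep the first of the month "if the resulting imputed date is greater than date of decision to discontinue study treatment".
- B: keep the first of the month "if the month is before the month of date of decision to discontinue study treatment and year is same or before the year" of the decision.
- C: "Otherwise set the imputed date to date of decision to discontinue study treatment + 1".

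When the month is unknown, a year after the decision year gives 1 January and a year equal to it gives decision + 1. A year before the decision year is not mentioned.

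The imputed date is used in several places. In the primary PFS definition (SAP 7.1.1.4), subjects who receive systemic or local NPACT before an event "will be right censored at the date of the last tumor assessment prior to the date of initiation of subsequent therapy/surgery". Table 8 repeats this for PFS-EP-1 as "date of last ATA* before first initiation of therapy". The best-response window in SAP 7.5.1 closes at the same censoring events. In the supportive OS analysis OS-EA1-1 (SAP 7.1.2.6), a subject on such therapy "will be right censored at the first start date of such subsequent anticancer therapy".

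**The concern.** Branch B mentions earlier years, so starts before the decision year were evidently meant to be kept where the site recorded them. The month test defeats this whenever the decision falls early in a year and therapy began late in the year before. The imputed date then contradicts data actually recorded.

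The adverse event onset rule in the same appendix nests the month test inside the year test and does not have this fault. The SAP addendum covers excess events and information fractions only, so nothing elsewhere corrects it.

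If the start date is pushed late, tumor assessments made after the true start are kept. A BIRC progression or a death in the gap then counts as a PFS event when the subject should already have been censored.

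**Working it through.** There is no figure in the plan to reproduce, because this is date logic. Let (y, m) be the recorded year and month and D the decision date. As written, the imputed date is the first of (y, m) if that date is after D, or if m < month(D) and y ≤ year(D). Otherwise it is D + 1.

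**Examples under the rule as written**

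| Recorded | Decision | Imputed | Days after first / last day of recorded month |
|---|---|---|---|
| Dec 2020 | 10 Feb 2021 | 11 Feb 2021 | 72 / 42 |
| Nov 2020 | 15 Feb 2021 | 16 Feb 2021 | 107 / 78 |
| Dec 2020 | 15 Jan 2021 | 16 Jan 2021 | 46 / 16 |
| Feb 2020 | 15 Feb 2021 | 16 Feb 2021 | 381 / 353 |
| Jan 2020 | 15 Feb 2021 | 1 Jan 2020 | kept |
| Jan 2021 | 15 Feb 2021 | 1 Jan 2021 | kept |

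For the first row, 1 December is not after the decision (A fails) and 12 is not below 2 (B fails), so C applies.

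**Which earlier-year starts are moved.** Take a start in the year before the decision year, with the decision on the 15th (an assumption). There are 12 × 12 = 144 month pairs. A start is moved when m ≥ month(D), which gives 12 + 11 + … + 1 = 78 pairs. The gap in months is 12 + month(D) − m, so m ≥ month(D) is the same as a gap of 12 months or less. All 78 such pairs are moved and none of the other 66. Starts in an earlier month of the decision year are never moved. With a joint comparison, (y, m) < (year(D), month(D)), none of the 144 is moved.

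**Share moved, given a day-missing start L days before the decision.** Assume decision dates are spread evenly over 365 days. The start falls in the previous calendar year when the decision's day of the year is at most L, so the share is L/365:

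- L = 30: 30/365 = 8.2%
- L = 60: 60/365 = 16.4%
- L = 90: 90/365 = 24.7%

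At L = 30 a further 7 decision dates, (30 + 7)/365 = 10.1% in all, also give a date outside the recorded month. These are decisions on the 31st with a start on the 1st of the same month, where decision + 1 spills into the next month. That comes from the same-month branch and not from the separate month and year tests.

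**Length of the gap.** The imputed date is L + 1 days after the true start: 31, 61 or 91 days. Protocol 5.8.6.2 says "Tumor assessments after randomization should be performed every 6 weeks" through Week 49. In units of 42 days the gaps are 0.7, 1.5 and 2.2 scan intervals, so a 91-day shift spans two to three nominal scans.

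**The case against.** The strongest reply is that this seldom reaches the endpoint. Protocol 3.5.1 makes the need for systemic NPACT a reason to withdraw study treatment, and Protocol 7.2 prohibits it until treatment has stopped, so a systemic start before the decision should be rare. Protocol 7.2 also asks that local therapy wait until radiographic progression, and in many such subjects the PFS event will already have occurred. This largely stands. What remains is that the progression in question is the investigator's, treatment and scans may continue after it (Protocol 5.8.6.3 and Table 4), and PFS-EP-1 uses BIRC progression. A subject with investigator but not BIRC progression can receive local therapy on treatment and be scanned again.

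A second reply is that month could be read as calendar month and year together. That reading removes the error but makes the year clause redundant, and a programmer following the text would not necessarily adopt it.

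A reader might infer that the date error runs equally through every analysis that uses NPACT. It does not. In PFS-EA2-1 only systemic NPACT is an event, and local NPACT is censored. OS-EA1-1 concerns medications and not radiation. Table 8 excludes local radiation from NPACT, and the documents do not show whether radiation is recorded on the form that this rule covers.

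**Conclusion.** The rule is wrong as written, at minor severity. It moves day-missing starts from an earlier calendar year, up to 12 months before the decision, to decision + 1. Separately, it gives no instruction for year-only dates before the decision year.

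The 8%, 16% and 25% shares are conditional on a missing day and a pre-decision start, and on evenly spread decision dates. The documents give no count of such records; they are likely few and mainly local NPACT begun on treatment. PFS-EP-1 changes only for a subject who is event-free per BIRC at the true start and has a scan or event in the gap.

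Two stronger readings are not supported. One is that all therapy begun in an earlier calendar year is moved; starts more than 12 months before the decision keep their recorded month. The other is that primary PFS is biased towards one arm; nothing in the documents fixes the direction, and no change in the primary result is shown.

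**What to change.** Replace the day-missing text with a joint year-month comparison:

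- Recorded year-month before or after the decision's year-month: use the first of the recorded month.
- Same year-month: use decision + 1, capped at the last day of that month.
- Only the year known, and before the decision year: use 1 January.
- In every case, impute no earlier than randomization + 1.
- No discontinuation decision date, as may arise for subjects never treated (inferred, since the forms are not shown): use the first of the recorded month with the same floor.

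The floor matters. Without it, a subject randomized on 20 December 2020 with therapy recorded as December 2020 and a decision on 10 February 2021 would get 1 December 2020, before randomization. PFS would then be censored at randomization, OS-EA1-1 would have a negative time, and the therapy would no longer count as subsequent under SAP 4.7. With the floor the date is 21 December 2020.

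The cost is a short wording change and the matching programming. SAP 4.9 already allows clarifications and minor corrections by addendum before the final analyses. Making it in advance also avoids an ad hoc programming decision in an open-label trial where the sponsor knows the assignments (SAP 2.4).

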Appendix B: Rounding Rules for Reported Percentages

For percentages $\geq 10\%$:

- Values $\geq X.5$ or above round to $X+1$.
- Values $>X$ but $<X.5$ round to X .

For percentages $<10\%$:

- Values $\geq X.Y5$ or above round to $X.Y+0.1$.
- Values $>X.Y$ but $<X.Y5$ round to $X.Y$.

Appendix C: Imputation Rules for Laboratory Values Outside of Quantification Range

- Lab values below the lower level of quantification (LLQ) that are reported as “< LLQ” or “≤ LLQ” in the database will be imputed by $LLQ \times 0.99$ for analysis purposes. However, the original value will also be maintained.
- Lab values above the upper level of quantification (ULQ) that are reported as “> ULQ” or “≥ ULQ” in the database will be imputed by $ULQ \times 1.01$ for analysis purposes. However, the original value will also be maintained.

Appendix D: EQ-5D-5L Index Value Conversion Guidelines

The EQ-index conversion algorithm (EQ-5D-5L User Guide 2.1, April 2015. Available from: <http://www.euroqol.org/about-eq-5d/publications/user-guide.html>):

- Calculate ***health state***
 - Each of the 5 dimensions comprising the EQ-5D descriptive system is divided into 5 levels of perceived problems:
 - Level 1: indicating no problem
 - Level 2: indicating slight problems
 - Level 3: indicating moderate problems
 - Level 4: indicating severe problems
 - Level 5: indicating extreme problems
 - A unique health state is defined by combining 1 level from each of the 5 dimensions.
For example, state 11111 indicates no problems on any of the 5 dimensions, while state 12345 indicates no problems with mobility, slight problems with washing or dressing, moderate problems with doing usual activities, severe pain or discomfort and extreme anxiety or depression. Note that missing values will be coded as '9'. Ambiguous values will be treated as missing values.
- ***EQ-index values*** for each country = ***health state * the country specific conversion factors*** for each dimension (EQ-5D-5L Index Value Calculator, version 1)

